## Intervention:

Active arm) 3cc bupivacaine 0.5% to be injected into the greater occipital nerve region bilaterally  
Sham arm) 0.5cc bupivacaine 0.5% to be injected intradermally in the posterior scalp bilaterally

Formal training sessions will be conducted for those who will inject for research purposes.

Step-by-step procedure for performing bilateral occipital nerve block or sham injection

1. Eligible patient identified.
2. Consent obtained.
3. Research associate hands provider assignment envelope, bottle of 0.5% bupivacaine, 10cc syringe, 27 gauge needle, 2 alcohol swabs and then goes away
4. Provider opens envelope, reads assignment, destroys paper containing assignment
5. Provider draws 3cc bupivacaine into syringe
- 6a. If patient is randomized to active intervention, provider performs GONB: 1) identify occipital protuberance and mastoid process 2) insert 3 cc bupivacaine 1/3 of distance lateral to occipital protuberance, within groove, using fan technique. Repeat procedure on opposite side.

6b. If patient is randomized to sham intervention, provider performs intradermal injection: 1) identify occipital protuberance and mastoid process 2) insert 0.5 ccc bupivacaine intradermally 1/3 of distance lateral to occipital protuberance

7. Provider discards all supplies and summons research associate.

Randomization and Blinding: Study participants and outcome assessors will be blinded. Because the technique will vary depending on assignment, the clinician performing the procedure will not be blinded. A randomization list will be generated using an online generator at <http://www.randomization.com>. Participants will be assigned to active or sham arm in a 1:1 ratio. Assignment will be stratified on baseline pain intensity. Assignment will be placed in an opaque, sealed envelope with sequential study IDs written on the outside. Research personnel will hand the next sequential envelope to the clinician, who will read the assignment and then shred the envelope and its contents. We will give active agent to both study groups to ensure subject blinding. We hope subjects are more likely to believe they got active agent if part of their scalp is numb.

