Protocol: After obtaining informed consent, a brief pain assessment will be performed. A clinician will then inject bilateral GONs (Appendix 1). Research associates will ascertain the patient’s headache level 15, 30, 60, and 120 minutes post-injection. We will ask about the frequency of adverse events 30 minutes after the injection. We will also perform an assessment of light touch and allodynia before and after the procedure (Appendix 2 and Figure). Research associates will contact subjects by telephone 48 hours after ED discharge to ascertain headache status, satisfaction with treatment, and presence of adverse events.

Sample Size calculation: We chose a frequency of headache freedom of 50% as the lowest frequency of success for which clinicians would be willing to perform this procedure. We hope to minimize the placebo effect on the primary outcome by requiring headache freedom rather than just headache improvement. It is unlikely that a patient would progress from moderate/ severe headache to headache freedom within 30 minutes without intervention. We estimated a placebo rate of headache freedom of 20%. Using an alpha of 0.05 and a beta of

0.20, we calculated the need for 39 subjects in each arm. The study will continue until 78 patients have provided primary outcome data.

Analysis: The primary outcome is the rate of headache freedom at 30 minutes. Absolute risk reduction and number needed to treat will be reported with 95%CI. All dichotomous secondary outcomes will be reported as frequencies with 95%CI. Improvement in numerical rating scale will be reported as mean with 95%CI. The primary goal of this analysis is to demonstrate efficacy. If we do not demonstrate statistically significant differences but do see a signal through the noise, we will use the point estimates to decide the feasibility of another study. We will determine the between-group difference (absolute risk reduction) in rates of headache freedom and report this with 95%CI.

Data safety and monitoring: The goal of the data safety committee will be to review study protocol and adverse events on an ongoing basis to determine if risk to subjects can be minimized further without compromising study integrity. Because the overall sample size is relatively small and it will be important to report our findings with sufficient precision, the study will not be halted early for efficacy or futility.

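### Randomisation is stratified on baseline pain, but the primary analysis has no stratum term, so some power may be forgone; the NNT interval also needs a rule for when the difference interval includes 0.

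*Combined protocol and SAP*

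**What the plan says.** Methods, Randomization and Blinding: "Assignment will be stratified on baseline pain intensity", and "Participants will be assigned to active or sham arm in a 1:1 ratio". The scale, the cut-point, the number of strata and any blocking are not given. The envelopes are described as one sequential series.

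Methods, Analysis: "We will determine the between-group difference (absolute risk reduction) in rates of headache freedom and report this with 95%CI". The same paragraph adds: "Absolute risk reduction and number needed to treat will be reported with 95%CI". It names no stratified or adjusted method, covariate, test or interval formula. It foresees a non-significant result, in which case point estimates would guide whether another study is feasible. It has no rule for the NNT in that case.

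Methods, Sample Size calculation: "We chose a frequency of headache freedom of 50% as the lowest frequency of success", and "We estimated a placebo rate of headache freedom of 20" per cent. Then "Using an alpha of 0.05 and a beta of" "0.20, we calculated the need for 39 subjects in each arm".

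**The concern.** Entry requires persistent moderate or severe headache, and the outcome is no headache on the same ordinal scale 30 minutes later. Reaching none is plausibly easier from moderate than from severe, and stratifying on pain suggests that the investigators expect it to matter.

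When balance within strata is forced, between-stratum variation drops out of the treatment difference. An unstratified standard error still includes it. The test then rejects too rarely under the null and gives up some power, and the precision bought at randomisation goes unused in a trial of 78 patients.

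The NNT is the reciprocal of the difference. If the interval for the difference includes 0, inverting its two limits gives a pair of numbers that does not bracket the NNT. The plan promises an NNT interval without saying what happens then.

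**Working it through.** **Inputs from the protocol.** 50% v 20% headache freedom, alpha 0.05 (taken as two-sided, which reproduces the stated size), power 80%, 39 per arm, 1:1 allocation.

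**Assumptions.** Two equal strata, near-equal allocation within each, and the same gap between strata in both arms. The protocol gives no stratum-specific rates, so a range of gaps is shown.

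**1. The plan's own figure.** With the pooled-variance formula and mean rate 0.35:

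n = [1.960·√(2·0.35·0.65) + 0.8416·√(0.5·0.5 + 0.2·0.8)]² / 0.30² = (1.322 + 0.539)² / 0.09 = 38.5, so 39 per arm.

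Power at 39 per arm is 80.5%. The calculation reproduces exactly and is unstratified.

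**2. Why the unstratified standard error is too large.** With two equal strata and gap g, the binomial variance in an arm is p(1−p) = (mean within-stratum variance) + (g/2)². Under forced balance only the first term is real sampling variation.

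- At 50% v 20% and g = 0.30, the unstratified SE is √[(0.25 + 0.16)/39] = 0.1025. Removing 0.0225 per arm gives √(0.365/39) = 0.0967. The 95% half-widths are 20.1 and 19.0 points.
- At g = 0.20, 0.01 per arm is removed: √(0.39/39) = 0.100, half-width 19.6 points.
- Under the null (20% in both arms) and g = 0.30, the ratio of SEs is √(0.32/0.275) = 1.079. The effective critical value is 1.96 × 1.079 = 2.11, so two-sided type I error is about 3.5%.

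**3. Simulation.** 78 patients, Pearson chi-square v Cochran-Mantel-Haenszel (CMH):

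| Gap between strata | Active; sham rates | Power, chi-square | Power, CMH | Type I error, chi-square | Type I error, CMH |
|---|---|---|---|---|---|
| 0 | 50/50; 20/20 | 81.2% | 80.5% | 5.0% | 5.0% |
| 10 points | 55/45; 25/15 | 81.4% | 81.1% | not tabulated | not tabulated |
| 20 points | 60/40; 30/10 | 81.7% | 82.6% | 4.5% | 5.0% |
| 30 points | 65/35; 35/5 | 82.4% | 85.2% | 3.6% | 4.9% |

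Type I error uses the sham rates in both arms. Repeat simulations agreed to within 0.4 points. The gain from stratifying is 82.6 − 81.7 = 0.9 points at a 20-point gap and 85.2 − 82.4 = 2.8 points at 30. The cost with no stratum effect is 81.2 − 80.5 = 0.7 points.

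**4. Interval coverage.** An unstratified 95% Wald interval covers 94.2%, 94.3% and 94.9% at gaps of 0, 10 and 20 points, and 95.5% to 95.7% at 30. A simple Mantel-Haenszel Wald interval covers only about 93.5% to 94%, so the interval method has to be chosen along with the stratification.

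**5. NNT.** By exact binomial enumeration at 39 per arm, the Wald interval for the difference includes 0 in 17.4% of trials at 50% v 20%, 47.5% at 40% v 20% and 65% at 35% v 20%.

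Example: 15/39 v 8/39.

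- Difference 38.5% − 20.5% = 17.9 points, SE 0.1012, 95% CI −1.9 to 37.8.
- NNT = 1/0.179 = 5.6.
- Inverted limits: 1/0.378 = 2.6 and 1/(−0.0189) = −53. A range from −53 to 2.6 excludes 5.6.
- The correct set is NNT(benefit) from 2.6 up to infinity, together with NNT(harm) from 53 up to infinity.

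**The case against.** - **Size.** The gain is conditional and modest. A 30-point gap means 35% v 5% in the sham arm, a seven-fold difference. With equal strata and a 20% sham rate, the gap there cannot exceed 40 points. If the strata split 25/75, the gain at 30 points falls to about 2 (82.2% v 84.2%). At gaps of 0 and 10 points, stratifying loses a little. This stands.
- **Mechanism.** Stratifying does not by itself force balance, blocking is not stated, and the envelopes are one series. Without forced balance, the unstratified test has type I error of 5.0% to 5.2% at every gap. This stands too, although adjustment could still add power for a strongly prognostic stratum.
- **Silence.** The Analysis paragraph never calls its difference unadjusted. A simple difference in rates is the natural reading, but the charge is non-specification, not a declared wrong method.
- **NNT.** The plan does not commit to naive inversion, and it already reports the difference with its own interval. No stated decision uses the NNT interval. That makes this part a reporting convention.

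Three stronger readings might be inferred, and the documents support none of them. The intervals are not shown to be wrongly sized: Wald coverage stays close to 95% in the scenarios above, and any test error from the missing stratum is conservative. The trial is not underpowered for want of a stratum term, because 39 per arm was calculated without one. And the NNT interval does not cease to exist when the difference is not significant; it becomes two pieces joined at infinity.

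**Conclusion.** The point holds as a low-cost improvement. The design stratifies on baseline pain, and the primary analysis, as written, does not use the strata. If pain is prognostic and balance within strata is forced, the unstratified test is conservative and forgoes about 1 point of power at a 20-point gap and about 3 at 30, with type I error near 3.6% instead of 5% at 30. If pain is not prognostic, stratifying costs under 1 point. Power is above 80% in every scenario tabulated, with either test.

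These sizes rest on assumed stratum rates, equal strata and near-equal allocation within them. That the strata are moderate and severe is an inference from the entry criterion and the ordinal scale; the protocol also records a 0 to 10 scale and does not say which one defines them.

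The NNT gap does not depend on those stratum assumptions, but it is secondary.

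**What to change.** In Randomization and Blinding, define the strata (scale and cut-point) and state whether allocation is blocked within them.

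In Analysis, make the primary estimate the Mantel-Haenszel risk difference stratified by the baseline-pain strata used at randomisation (presumably moderate v severe), with a score-type 95% CI such as stratified Newcombe and the CMH test. Report the unstratified difference as supportive.

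Add one reporting rule: give the NNT with an ordinary interval only when the CI for the difference excludes 0. Otherwise report the difference alone, or the NNT as NNT(benefit) through infinity to NNT(harm).

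The cost is a few sentences, settled before unblinding. It needs no new data and no change to the sample size.

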### **Data Safety and Monitoring Section**

(i) A description of the types of data or events that will be captured by explaining:

- What safety information will be collected: *Adverse events will be collected in the ED and at 48 hour follow-up by asking a screening question: "Did you experience any side effects from the medication" followed by an open-ended query to have the patient explain.*
- How safety information will be collected: *Subject Interview*
- When data will be collected: *In ED, every 30 minutes, and by telephone 48 hours later.*

(ii) A plan for assuring data accuracy and protocol compliance. *Data will be reviewed by the PI after entry into REDCap.*

(iii) Timeframes for reporting adverse events and unanticipated problems to the monitoring entity. *The PI is the monitoring entity*

(iv) The frequency of monitoring entity's assessment of data or events. *After every enrollment.*

(v) The specific triggers or stopping rules: Conditions that would trigger an immediate suspension of the research. *No automatic triggers have been established.*

(vi) The procedures for communicating the outcome of the reviews by the Monitoring Entity to the IRB, and other appropriate entities. *All SAEs will be communicated to the IRB after review for causality by the PI. Other AEs will be communicated during annual review.*

Data Storage & Confidentiality: Data will be stored and maintained in REDCap. Data analysis will occur on password-protected computers. Consent documents will be maintained in locked research cabinets. Only study personnel will have access to the data and consent documents.

### Appendix 1. Step-by-step procedure for performing bilateral occipital nerve block or sham injection

1. Research associate identifies eligible patient.
2. Research associate obtains consent
3. Research associate hands provider assignment envelope (lowest available study ID), bottle of 0.5% bupivacaine, 10cc syringe, 27 gauge needle, 2 alcohol swabs. Research associate then returns to research desk.
4. Provider opens envelope, reads assignment, destroys paper containing assignment
5. Provider draws 6cc bupivacaine into syringe
- 6a. If patient is randomized to active intervention, provider performs GONB: 1) identify occipital protuberance and mastoid process 2) after negative aspiration insert 3 cc bupivacaine 1/3 of distance lateral to occipital protuberance, within groove, using fan technique. Repeat procedure on opposite side.
- 6b. If patient is randomized to sham intervention, provider performs intradermal injection: 1) identify occipital protuberance and mastoid process 2) insert 0.5 cc bupivacaine intradermally 1/3 of distance lateral to occipital protuberance
7. Provider discards all supplies and summons research associate.

### Appendix 2. Assessment of light touch and allodynia

Prior to procedure and 15 minutes after the procedure, research associates will assess light touch sensation and allodynia in 6 locations around the scalp: bilateral forehead, bilateral upper posterior scalp, and bilateral lower posterior scalp overlying the injection site (see figure). Using a piece of gauze, research associates will gently stroke each area 4 times and ask two questions: 1) Did you feel that? 2) Did that hurt?

[figure not shown]

Figure: Locations at which allodynia and light touch will be assessed before and after intervention

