## Methods.

**Study Overview:** This will be a randomized, double-blind clinical trial comparing an active treatment of acute migraine versus placebo in an emergency department after the standard of care for acute migraine has already been administered. The Albert Einstein College of Medicine IRB will provide ethical oversight. The trial will be registered at <http://www.clinicaltrials.gov>.

**Setting:** This study is to be performed in the emergency departments of Montefiore Medical Center. Salaried, trained, bilingual (English and Spanish) technician-level research associates, who execute research studies under the supervision of the principal investigators, staff the emergency department 24 hours per day/ seven days per week and will collect outcome data for this study.

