Methods of Measurement: As a primary measure of headache intensity, this study will utilize a standard ordinal headache intensity scale, in which subjects describe their headache as “severe”, “moderate”, “mild”, or “none”. We will also assess pain using an 11-point numerical rating scale (NRS). This latter scale asks subjects to assign their pain a number between 0 and 10, with 0 representing no pain and ten representing the worst pain imaginable. Both of these measures are recommended for use in migraine research by the International Headache Society. We will ascertain overall subject satisfaction with the experimental treatment by asking them if they want to receive the same treatment the next time they come to the ER with a migraine headache. Adverse events will be elicited using a dichotomous question (Did you have any side effects that were caused by the procedure?) followed by an open ended question (Please tell us about the side effects you experienced). Light touch will be assessed in the C2 dermatome. If done correctly, patients will be numb in GON distribution and hopefully migraine free. The number of previous GONB performed will be recorded.

Outcomes: The primary outcome will be the frequency of headache freedom (headache level = none) thirty minutes after completion of the procedure. Important secondary outcomes will be the frequency of sustained headache relief (achieving a pain level of mild or none within one hour of the procedure and maintaining a level of mild or none without the use of additional medication for 48 hours) and subject satisfaction, as evidenced by an affirmative response to the question, do you want to receive the same procedure the next time you come to the ER with migraine. We will also report the improvement in 0 – 10 pain scale between baseline and one hour and the frequency of adverse events.

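### The 15-minute scalp-sensation test, done by the staff who are meant to be blinded, can hint at the arm before the 30-minute primary rating and puts assessor blinding at avoidable risk

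*Combined protocol and SAP*

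**What the plan says.** The Randomization and Blinding paragraph states: "Study participants and outcome assessors will be blinded". The clinician who injects is not blinded. The Setting paragraph says that the research associates "will collect outcome data for this study", and the Protocol paragraph adds: "Research associates will ascertain the patient’s headache level 15, 30, 60, and 120 minutes post-injection". The primary outcome is a headache level of none at 30 minutes, on a four-category scale that the patient answers aloud.

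The procedure protects the associate from learning the assignment. In Appendix 1 the associate returns to the research desk before the envelope is opened, the assignment paper is destroyed, and the associate is called back only after the supplies are discarded.

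Appendix 2 then gives research associates a sensory examination: "Prior to procedure and 15 minutes after the procedure, research associates will assess light touch sensation and allodynia in 6 locations around the scalp". The sites are "bilateral forehead, bilateral upper posterior scalp, and bilateral lower posterior scalp overlying the injection site". At each site the associate strokes the skin with gauze and is to "ask two questions: 1) Did you feel that? 2) Did that hurt".

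On what numbness means, the Methods of Measurement paragraph says: "If done correctly, patients will be numb in GON distribution and hopefully migraine free". The active arm receives 3 cc of bupivacaine 0.5% on each side in the region of the nerve. The sham arm receives 0.5 cc on each side intradermally, at the same landmark.

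**The concern.** The plan removes the associate from the room so that the assignment stays unknown. Fifteen minutes later it has the same staff group collect the protocol's own physical sign of a correct block. That happens 15 minutes before the primary rating and ahead of the 60- and 120-minute ratings. Nothing in the plan assigns a different person to the test, withholds its result from whoever takes the headache rating, or checks afterwards whether assessors or patients could guess the arm.

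The primary endpoint depends on whether a spoken answer is taken as none or as mild. An assessor who suspects the arm can influence that through how the question is put, whether it is repeated, and how a hesitant answer is coded. Stroking six sites and asking whether each stroke was felt may also draw the patient's attention to how far the numbness extends. If either effect favours the block, the planned comparison of proportions can neither detect nor remove it.

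**Working it through.** **1. Order of events, from the documents**

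| Time after procedure | Event | Done by | Source |
|---|---|---|---|
| 0 | Associate called back, assignment not disclosed | Provider | Appendix 1, step 7 |
| 15 min | Light touch and allodynia at six sites | Research associate | Appendix 2 |
| 15 min | Headache level | Research associate | Protocol paragraph |
| 30 min | Headache level (primary outcome) and adverse events | Research associate (headache level) | Outcomes; Protocol paragraph |
| 60 min | Headache level; bears on sustained relief and on the one-hour change in the 0–10 score | Research associate | Outcomes; Protocol paragraph |
| 120 min | Headache level; inside the 48-hour sustained-relief window | Research associate | Outcomes; Protocol paragraph |
| 48 h after discharge | Telephone call | Research associate | Protocol paragraph |

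The sensory result is therefore known before every rating from 30 minutes on. None of the outcomes listed in the Outcomes paragraph uses it.

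**2. What the test can reveal**

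- Lower posterior scalp, over the injection site: both arms receive bupivacaine there, so numbness need not separate them.
- Upper posterior scalp, listed as a separate site: numbness here is more to be expected after a block of the nerve's distribution than after 0.5 cc intradermally. This is an inference from volume and route. The documents give no numbness rates by arm or site, and the figure that locates the sites is not available.
- Forehead: the documents give no reason to expect a difference in numbness.

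The hint therefore rests mainly on the upper posterior sites, and its strength is unknown.

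**3. The plan's sample size**

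Inputs from the Sample Size paragraph: 50% v 20%, alpha 0.05 (taken as two-sided), beta 0.20. With pooled proportion 0.35 and no continuity correction:

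n = [1.96·√(2·0.35·0.65) + 0.8416·√(0.5·0.5 + 0.2·0.8)]² / (0.5 − 0.2)² = (1.3221 + 0.5389)² / 0.09 = 38.5, which rounds up to 39 per arm.

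This matches the plan and is not in dispute.

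**4. Illustration of sensitivity to bias**

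The documents give no bias size, so the shifts below are assumptions. Take no true effect, 39 per arm and a true rate of 20% in both arms (the plan's sham rate). Let X and Y be the headache-free counts, binomial with n = 39 and reported rates p₁ (active) and p₂ (sham). The test is the two-sided pooled z test at 0.05:

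z = (X − Y)/39 ÷ √[p̄(1 − p̄)·2/39], with p̄ = (X + Y)/78.

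Summing the exact probabilities of all pairs with z > 1.96 gives the chance of a significant result favouring the block:

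| Reported rate, active v sham | Shift in patients (points × 39) | Chance |
|---|---|---|
| 20% v 20% | 0 | 2.5% |
| 22.5% v 20% | about 1 in the active arm | 4.6% |
| 25% v 20% | about 2 in the active arm | 7.7% |
| 30% v 20% | about 4 in the active arm | 17.7% |

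If bias also lowered reported freedom on sham, the figures would be higher: 8.0% at 22.5% v 17.5% and 19.6% at 25% v 15%. That requires sham patients to be recorded as worse than they are, a stronger assumption than the rows in the table.

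**The case against.** A reader might infer that the test shows which arm was given and that blinding is lost. The documents do not support that, for these reasons.

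- Both arms receive bupivacaine at the same landmark, and the sham is designed to leave part of the scalp numb. Numbness is also expected only if the block is done correctly, so its absence does not identify sham.
- No numbness rates are given, so how well the test separates the arms cannot be stated.
- The text names a role. It does not say that the individual who does the test also takes the 30-minute rating.
- The outcome is the patient's own choice among four words, so assessor knowledge acts only through the asking and recording.
- For patients the case is weaker still. They can notice a numb scalp without being tested, the documents do not say that they know which pattern belongs to which arm, and numbness in sham patients is meant to suggest active treatment. The test could therefore raise expectation in either arm.

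All of this stands, and it limits the claim to a risk. It does not remove the risk. Nothing prevents one associate from doing both tasks, and the outcome turns on the boundary between none and mild. The test also creates a dilemma. If it separates the arms, it weakens blinding. If it does not, it says little about whether the block worked. Neither case calls for doing it before the primary rating.

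**Conclusion.** The point holds as an avoidable and unchecked risk to assessor blinding, with a possible secondary effect on patients' expectations. The order of events and the absence of any separation between tester and rater are clear from the text. That the result can hint at the arm is a reasonable inference from the protocol's own description of a correct block and from the difference in volume and route.

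The size is unknown. The figures of 4.6%, 7.7% and 17.7%, against 2.5% without bias, show only how sensitive a trial of 39 per arm is to assumed shifts of about one, two or four patients in the active arm. They are not estimates of what would happen. The matter deserves correction before enrolment because the primary outcome is subjective, the trial is small, and the remedy is cheap.

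**What to change.** In Appendix 2 and the Protocol paragraph, move the post-procedure light-touch and allodynia test to after the 30-minute headache rating has been recorded and locked. Preferably, place it after the 120-minute rating, the last in-ED headache rating. Stopping at 60 minutes would not cover every rating that matters: the 60-minute rating feeds sustained relief and the one-hour pain change, and the 120-minute rating still lies within the 48-hour sustained-relief window. The test before the procedure can stay where it is.

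Where the existing rota allows, the 48-hour call should be made by an associate who did not do the sensory test. If a 15-minute sensory reading is considered essential, the alternative is a separate tester whose result is withheld from the rater, at the price of a second person.

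The main change is one of timing, in Appendix 2, the Protocol paragraph and the case report form, with no added procedure. The downside is that sensation is checked later than 15 minutes and some patients may leave before it, the more so if it waits until 120 minutes. The change does not stop patients from noticing or mentioning numbness themselves; it removes the point at which the plan makes the assessor look for it.
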